**NON-INTERVENTIONAL (NI) STUDY PROTOCOL**

**Study information**

Title	Overall survival (OS) in patients with metastatic BRAFV600-mutant melanoma treated with encorafenib plus binimatinib in the COLUMBUS trial versus in real-world practice data
Protocol number	C4221035
Protocol version identifier	1.0
Date	24 February 2023
Active substance	Encorafenib plus Binimatinib
Medicinal product	Braftovi® plus Mektovi®
Research question and objectives	
The study objective is to describe and compare OS in patients with metastatic BRAFV600-mutant melanoma treated with encorafenib plus binimatinib (ENCO+BINI) in the Phase 3 COLUMBUS clinical trial versus in real-world data (RWD) from Flatiron Health.
 
This study will help contextualize real-world clinical effectiveness of ENCO+BINI and assess the suitability of pooling clinical trial and RWD on ENCO+BINI from these two sources for use in future real-world studies.

Author(s)	PPD , PharmD PPD

This document contains confidential information belonging to Pfizer. Except as otherwise agreed to in writing, by accepting or reviewing this document, you agree to hold this information in confidence and not copy or disclose it to others (except where required by applicable law) or use it for unauthorized purposes. In the event of any actual or suspected breach of this obligation, Pfizer must be promptly notified.

## 2. LIST OF ABBREVIATIONS

Abbreviation	Definition
1L	first-line
AJCC	American Joint Committee on Cancer
BMI	body mass index
BRAF	v-Raf murine sarcoma viral oncogene homolog B protein
CI	confidence interval
CTD	clinical trial data
ECOG	European Cooperative Oncology Group
EHR	electronic health record
ENCO+BINI	Encorafenib + Binimetinib
ESMO	European Society of Medical Oncology
FDA	Food and Drug Administration
GPP	Good Pharmacoepidemiology Practices
GRACE	Good Research for Comparative Effectiveness
HIPAA	Health Insurance Portability and Accountability Act
HR	hazard ratio
ICD-9-CM	International Classification of Diseases 9th Revision Clinical Modification
ICD-10-CM	International Classification of Diseases 10th Revision Clinical Modification
IEC	Independent Ethics Committee
IO	Immunotherapy
IRB	Institutional Review Board
ISPE	International Society for Pharmacoepidemiology
ISPOR	International Society for Pharmacoeconomics and Outcomes Research
KM	Kaplan-Meier
LDH	lactate dehydrogenase
MAPK	mitogen-activated protein kinase

MICE	multivariate imputation by chained equations
NDI	National Death Index
NI	non-interventional
OS	overall survival
PFS	progression free survival
RECIST	Response Evaluation Criteria in Solid Tumours
RWD	real-world data
SAS	Statistical Analysis Software
SSDI	Social Security Death Index
TT	targeted therapy
US	United States

#### **4. AMENDMENTS AND UPDATES**

None.

## 5. MILESTONES

Milestone	Planned date
Completion of feasibility assessment	23 January 2023
Development of study protocol/statistical analysis plan	24 February 2023
Completion of statistical analyses	21 April 2023
Abstract submission to European Society of Medical Oncology (ESMO) 2023	10 May 2023
Final study report	02 June 2023

## 6. RATIONALE AND BACKGROUND

Melanoma, caused when malignant cancer cells form in melanocytes, is the fifth most common cancer in the United States (US) and the deadliest form of skin cancer. Incidence of melanoma has been increasing over recent decades, with the overall incidence rate of 229.1 cases per million person based on recent estimates. Based on American Cancer Society estimates, there were an estimated 99,780 new cases of melanoma and ~7,650 deaths from melanoma in the US in 2022.

Approximately 9% of melanoma patients are diagnosed with regional spread to lymph nodes and 4% are diagnosed with metastatic disease. Compared to patients with localized melanoma, patients with metastatic melanoma have poorer prognosis and worse outcomes, which can be further worsened by the presence of v-Raf murine sarcoma viral oncogene homolog B protein (BRAF) mutations. The BRAF protein plays an important role in normal cell growth, proliferation, differentiation, and survival. The presence of BRAF V600 mutations, found in ~40–60% of melanoma cases, can lead to sustained mitogen-activated protein kinase (MAPK) pathway signaling, resulting in tumor growth and progression.

Recommended treatment options for metastatic melanoma include immunotherapy (IO), which attempts to stimulate host responses to effectuate tumor destruction, and targeted therapies (TT), which inhibit molecular pathways to prevent tumor growth and maintenance. The discovery of targeted therapy as a treatment for melanoma has emerged as a milestone development in oncological research. In 2018, the US Food and Drug Administration (FDA) approved the use of encorafenib (BRAFTOVI®) in combination with binimatinib (MEKTOVI®) for the treatment of patients with unresectable or metastatic melanoma with a BRAF V600E or V600K mutation (as detected by an FDA-approved test) based on the pivotal phase 3 COLUMBUS trial.

There is increasing interest in using real-world data (RWD) to evaluate effectiveness of encorafenib plus binimatinib (ENCO+BINI). One important use of the emerging RWD for ENCO+BINI is to assess how clinical effectiveness in real-world practice compares to efficacy observed in clinical trials. Clinical trial data (CTD) and real-world data on ENCO+BINI may also be pooled to provide a larger sample size for future evidence generation studies, provided outcomes are sufficiently consistent between CTD and RWD settings.

However, use of RWD presents important challenges. In general, differences in baseline characteristics between patients enrolled in clinical trials and patients receiving treatment in RWD settings can result in bias. While this concern can be mitigated with adequate statistical adjustment, missing data in RWD sources on key confounders of outcomes may also hamper ability to adjust for such baseline differences. Suitability of RWD for specific uses therefore needs to be assessed on a case-by-case basis considering details of the RWD data source and outcomes of interest.

In this study, we will compare overall survival (OS) between patients receiving ENCO+BINI in the Phase 3 COLUMBUS trial versus in the Flatiron Health Electronic Health Records (EHR) database. Baseline profiles of patients will also be compared across these settings to characterize differences in patients receiving ENCO+BINI and adjustments will be made for differences in baseline factors associated with OS. Missingness for key baseline characteristics will be addressed using a multiple imputation approach that has been validated for Flatiron Health EHR data in metastatic melanoma. This study will help contextualize real-world clinical effectiveness of ENCO+BINI, and assess the

suitability of pooling CTD and RWD on ENCO+BINI from these 2 sources for use in future RWE studies.

## 7. RESEARCH QUESTION AND OBJECTIVES

### Primary Objective

To compare OS between patients with metastatic BRAFV600-mutant melanoma initiating ENCO+BINI in the COLUMBUS Phase 3 trial versus Flatiron Health real-world practice data.

### Exploratory Objective

To compare progression-free survival (PFS) between patients with metastatic melanoma initiating ENCO+BINI in the COLUMBUS Phase 3 trial versus Flatiron Health real-world practice data.

This objective is designated as exploratory in this study as, unlike for OS, differences in assessment of PFS between trial and RWD settings may exist that preclude valid comparisons of this outcome across these settings. Suitability of comparative analyses of PFS will be determined following additional data exploration to characterize number and frequency of assessments of PFS available in RWD vs in CTD, and discussion of comparability of the assessment of disease progression in RWD vs CTD.

## 8. RESEARCH METHODS

### 8.1. Study design

This is a retrospective cohort study comparing OS outcomes between patients with BRAFV600-mutant metastatic melanoma initiating ENCO+BINI in the COLUMBUS clinical trial versus real-world practice data extracted from the Flatiron Health EHR database. Comparisons will be adjusted for differences in baseline characteristics across ENCO+BINI patients in these settings, and account for missing data on adjustment factors in the Flatiron Health EHR database. PFS will also be investigated as an exploratory endpoint, subject to comparability of outcome assessment between these 2 settings.

### 8.2. Setting

Patients with BRAFV600-mutant metastatic melanoma initiating treatment with ENCO+BINI will be included from the COLUMBUS clinical trial and from RWD extracted from the Flatiron Health EHR database.

#### 8.2.1. Inclusion criteria

Inclusion criteria are provided separately for the 2 data sources below. Key inclusion criteria in the COLUMBUS trial were:

- Histologically confirmed diagnosis of locally advanced, unresectable, or metastatic cutaneous melanoma or unknown primary melanoma

- American Joint Committee on Cancer (AJCC) disease stage of IIIB, IIIC, IVM1a, IVM1b, or IVM1c at trial enrolment
- Presence of BRAF V600E or V600K mutation in tumor tissue prior to enrollment
- At least 18 years of age at randomization
- Eastern Cooperative Oncology Group (ECOG) status of 0 or 1 at randomization
- Treatment naive or had progressed on or after previous first-line (1L) immunotherapy at randomization

Patients from the COLUMBUS trial included in this analysis will be those patients:

- Randomized to ENCO+BINI arm of the trial to receive 450mg once daily encorafenib and 45mg twice daily binimatinib combination therapy, and
- With available data on mortality

Pfizer has contracted with Flatiron for a custom data extract containing information on patients with advanced melanoma. Key inclusion criteria from the COLUMBUS trial will be applied to the Flatiron RWD population to align the populations to the extent possible between the 2 data sources.

Eligibility criteria applied to the Flatiron custom data extracted received by Pfizer included:

- Diagnosis of melanoma (International Classification of Diseases 9th or 10th Revision Clinical Modification - ICD-9-CM: 172.X; ICD-10-CM: C43.x) and secondary malignancy or metastasis (ICD-9-CM: 196.x, 197.x, 198.x; ICD-10-CM: C77.x, C78.x, C79.x).
- Confirmed BRAF V600E/V600K activating mutation reported in the data based on laboratory or genetic analysis results.
- At least 1 order or administration of ENCO+BINI treatment after the diagnosis of metastatic melanoma and within the available data cut period (01 January 2011 to 01 January 2022)
- Order or administration of ENCO+BINI treatment at least 3 months prior to the data cutoff date (e.g., 01 October 2022)

The sample of patients from the Flatiron health EHR data for this study will be identified using the following additional criteria applied to the custom data cut received from Flatiron:

- At least 1 order or administration of ENCO+BINI treatment after the diagnosis of metastatic melanoma and after 27 June 2018 (FDA approval date for ENCO+BINI for use in patients with metastatic melanoma); the date of the first such order or administration of ENCO+BINI will be taken as the **index date**.
- At least 18 years of age at the index date
- Treatment-naive or had previous 1L IO at index date, based on review of medication orders or administration prior to the index date.
- ECOG status of 0 or 1 at the index date

- With available data on mortality

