### 8.2.2. Exclusion criteria

Patients meeting any of the following criteria will not be included in the study:

- Patients without information on mortality
- Patients with ECOG performance status  $\geq 2$  (at the time of randomization for patients from COLUMBUS, during the baseline period for patients in Flatiron EHR)
- Patients with a history of or concurrent uveal or mucosal melanoma, basal cell or squamous cell carcinoma (as per trial inclusion criteria); this exclusion will also be applied to RWD patients
- For RWD patients, concurrent enrollment in a clinical trial.

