### 8.3. Variables

**Table 1** provides a summary of exposure, outcome, and patient baseline characteristics that will be evaluated within the study.

**Table 1.** Key exposures, outcomes, and patient baseline characteristics in the COLUMBUS trial data and Flatiron Health EHR data

Variable	Role	Data source(s)	Operational definition
ENCO+BINI Cohort (Columbus or Flatiron)	Exposure	Columbus trial data; Flatiron EHR	Binary variable indicating whether ENCO+BINI patients are derived from the Columbus trial data vs. Flatiron EHR population
OS	Primary Outcome	Columbus trial data, Flatiron EHR	In Columbus trial data, defined as the time from the date of randomization to the date of death due to any cause; if death is not observed, patients will be censored at the date of last contact or the data analysis cut-off date (e.g., 15 September 2020), whichever occurs first  In Flatiron EHR, defined as the time from the index date to the date of death; patients without a date of death will be censored at their last known activity date (e.g., the last clinical note date) or the end of the follow-up period whichever occurs first
PFS	Exploratory Outcome	Columbus trial data, Flatiron EHR	In Columbus trial data, defined as the time from the date of randomization to the date of the first documented disease progression or death due to any cause, whichever occurred first; if a patient did not have an event at the analysis cut-off date, PFS will be censored at the date of the last adequate tumour assessment  In Flatiron EHR, defined as the time from the index date to either the date of first disease progression event or death in the absence of progression; patients without disease progression or death will be censored at the last date the

PFIZER CONFIDENTIAL

			patient could have been assessed for progression (e.g., the last clinical note date) or the end of the study period (e.g., 01 January 2022), whichever occurs first
Age at index	Baseline Characteristic / Potential Confounder	Columbus trial data; Flatiron EHR	Patient age; defined at the time of study randomization for Columbus trial data and treatment initiation for Flatiron EHR
Sex	Baseline Characteristic / Potential Confounder	Columbus trial data; Flatiron EHR	Male, Female, Intersex, and Unknown/Missing
Race	Baseline Characteristic / Potential Confounder	Columbus trial data; Flatiron EHR	Asian, Black, White, Other/Multirace, and Unknown/Missing

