#### 8.4. Data sources

##### COLUMBUS trial

COLUMBUS was a two-part, multicenter, randomized, open-label, Phase 3 clinical trial. Part 1 of the trial investigated the effectiveness and safety of three treatment regimens in patients with locally advanced unresectable or metastatic BRAFV600-mutant metastatic melanoma who were treatment naïve or whose cancer had progressed after 1L IO. In Part 1 of the trial, patients were randomized to one of three treatment arms: 1) 450mg once daily encorafenib and 45mg twice daily binimatinib (n=192), 2) 960mg twice daily vemurafenib (n=191) and 3) 300mg once daily encorafenib (n=194). Randomization was stratified by AJCC disease stage (IIIB, IIIC, IVM1a, IVM1b, or IVM1c), ECOG performance status (0, 1), and BRAFV600 mutation profile (V600E, V600K). Progression-free survival was the primary endpoint in the trial, while OS was one of the secondary endpoints. Patients were enrolled in Part 1 of the trial between 30 December 2013 through 10 April 2015.

The ENCO+BINI arm of Part 1 of the trial will be used in this study (database lock date: 15 September 2020). Part 2 of the trial compared encorafenib 300mg once daily plus binimatinib 45mg twice daily versus encorafenib 300mg once daily alone and will not be considered.

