Treatment-Related Characteristics		
Prior therapies, n (%)		
Treatment naive	XX (XX.X)	XX (XX.X)
Disease progression after 1L IO	XX (XX.X)	XX (XX.X)
Prior systemic therapies, n (%)		
Any therapy	XX (XX.X)	XX (XX.X)
Medication	XX (XX.X)	XX (XX.X)
Surgery	XX (XX.X)	XX (XX.X)
Radiotherapy	XX (XX.X)	XX (XX.X)

**Appendix Table 2:** Kaplan-Meier analyses comparing OS between ENCO+BINI cohorts in Columbus trial and Flatiron RWD

	Columbus Trial	Flatiron RWD
	ENCO+BINI	ENCO+BINI
	N =	N =
Summary of deaths, censoring and median survival		
Death, n (%)	XX (XX.X)	XX (XX.X)
Censored, n (%)	XX (XX.X)	XX (XX.X)
Median OS (95% CI)	XX (XX, XX)	XX (XX, XX)
Kaplan-Meier based estimates of % of patients remaining alive at different time points		
6 Months	XX	XX
12 Months	XX	XX
18 Months	XX	XX
24 Months	XX	XX
30 Months	XX	XX
36 Months	XX	XX

**Appendix Table 3:** Unadjusted and adjusted hazard ratios comparing OS between ENCO+BINI cohorts in Columbus trial and Flatiron RWD

Results from adjusted models in Appendix Table 3 will be based on multiple imputation via multivariate imputation by chained equations. Expected adjustment factors are listed below; specific functional forms/categorization of adjustment factors will be based on the data.

	Unadjusted model	Adjusted model
	HR (95% CI)	HR (95% CI)
Exposure variable		
ENCO+BINI in Columbus trial (ref. ENCO+BINI in Flatiron RWD)	X.XX (X.XX, X.XX)	X.XX (X.XX, X.XX)
Adjustment factors		
Age	-	X.XX (X.XX, X.XX)
Male vs female	-	X.XX (X.XX, X.XX)
Race	-	X.XX (X.XX, X.XX)
BMI		
Disease stage	-	X.XX (X.XX, X.XX)
ECOG	-	X.XX (X.XX, X.XX)
LDH	-	X.XX (X.XX, X.XX)
Time from first diagnosis to metastatic disease...		X.XX (X.XX, X.XX)
Time from metastatic disease to treatment initiation		
Use of prior therapies		X.XX (X.XX, X.XX)

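### The Flatiron eligibility rule drops the trial's condition that patients pretreated with immunotherapy had progressed on or after it, so the pretreated strata may not be comparable

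*Combined protocol and SAP*

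**What the plan says.** Section 8.2.1 lists the trial's criterion for prior treatment as "Treatment naive or had progressed on or after previous first-line (1L) immunotherapy at randomization". Section 8.4 restates it for Part 1 of COLUMBUS: "treatment naïve or whose cancer had progressed after 1L IO". In both places a patient pretreated with IO must have progressed.

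The additional Flatiron criteria in Section 8.2.1 require that the patient be "Treatment-naive or had previous 1L IO at index date, based on review of medication orders or administration prior to the index date". No progression condition is attached. The stated purpose of the selection is alignment: "Key inclusion criteria from the COLUMBUS trial will be applied to the Flatiron RWD population to align the populations to the extent possible".

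The exclusions in Section 8.2.2 concern mortality data, ECOG status, other tumour types and concurrent trial enrolment. None concerns the outcome of earlier IO. Table 1 in Section 8.3 defines prior immunotherapy as a binary variable, and Section 8.7.4 lists use of prior therapies among the expected adjustment factors. Appendix Table 1 gives two rows under prior therapies for both cohorts: treatment naive, and "Disease progression after 1L IO".

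**The concern.** The two cohorts are selected on the same point by different rules, although the plan sets out to align them. An order or administration record establishes that IO was given. It does not establish that the disease progressed. A Flatiron patient who stopped IO for another reason meets the real-world rule but not the trial rule.

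The primary objective compares overall survival between the cohorts, and the result is meant to inform whether trial and real-world data can be pooled. A difference in who counts as pretreated feeds into that comparison. It lies within the IO-pretreated stratum, so adjusting for membership of the stratum leaves it in place. The shell adds a reporting problem: its second row describes Flatiron patients by a status that the selection rule does not check, and a reader of the finished table would see an agreement between cohorts that had not been established.

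**Working it through.** **Side-by-side reading**

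| Element | COLUMBUS | Flatiron |
|---|---|---|
| Treatment-naive patients | Admitted | Admitted |
| Prior 1L IO | Admitted only after progression on or after it | Admitted on exposure alone |
| Evidence named | None given in this plan | Medication orders or administrations |
| Number of prior lines | Not stated beyond 1L IO | Not stated beyond 1L IO |
| Row in Appendix Table 1 | Progression after 1L IO | Same row |

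The rules differ in the second line of the table, and nothing elsewhere in the plan restores the condition. Section 8.9 names diagnosis, stage, age, BRAF mutation and ECOG as the aligned criteria and does not name prior therapy. Its limitations disclose that the RECIST measurable-lesion criterion cannot be applied, but not that this condition is missing.

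**Size**

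The plan states no figure to reproduce: Section 8.5 gives no sample size, and no share of pretreated patients appears anywhere. The following is for scale only, and all three inputs are assumptions.

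- p = share of Flatiron patients with prior IO: 0.30 to 0.60.
- q = share of those without progression: 0.15 to 0.30.
- h = their hazard of death relative to the rest of the cohort: 0.6 to 0.8, taking the rest of the cohort to have one common average hazard.

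Relative to a cohort that meets the trial's rule, the average Flatiron hazard at the start of follow-up is 1 − p·q·(1 − h). Flatiron is the reference group in Appendix Table 3, so the trial-versus-Flatiron HR is multiplied by the reciprocal:

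multiplier = 1 / [1 − p·q·(1 − h)]

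- Low end: 1 / (1 − 0.30 × 0.15 × 0.2) = 1 / 0.991 = 1.01.
- In between (p = 0.4, q = 0.3, h = 0.6): 1 / (1 − 0.048) = 1.05.
- High end: 1 / (1 − 0.60 × 0.30 × 0.4) = 1 / 0.928 = 1.08.

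Within the IO-pretreated stratum alone, p drops out and the same inputs give 1 / (1 − 0.15 × 0.2) = 1.03 to 1 / (1 − 0.30 × 0.4) = 1.14. A yes/no term for prior IO compares patients within strata, so it does not remove this factor from the pretreated stratum.

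**The case against.** The plan promises alignment only as far as possible, and it adjusts for ECOG, LDH, stage and time from metastatic diagnosis to treatment as well as prior therapy. Those covariates may absorb part of the difference. The shell is an unfilled template, and its wording may equally show that the sponsor intended the trial's condition and that the Flatiron bullet abbreviates it. These points stand. They limit the likely effect and support reconciling the passages, but they do not put the condition into the selection rule.

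Some stronger readings are tempting, and the documents do not support them.

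- *The pretreated groups do differ.* The definitions differ. No counts are given, so it is not known whether the groups do.
- *The Flatiron rule lets in later-line patients whom the trial excluded.* The trial's criterion as printed is equally silent on later lines, and the Flatiron wording can be read as 1L IO only. This is an ambiguity, not a shown difference between the cohorts, and no bias should be attributed to it.
- *Progression must be available because the plan uses Flatiron progression dates for PFS.* That endpoint is "time from the index date to either the date of first disease progression event or death in the absence of progression". It concerns progression after the index date and does not show that progression on earlier IO was recorded. Whether it was cannot be told from the documents.
- *The primary cohort should require documented progression and no other systemic therapy.* The first depends on unconfirmed ascertainment before index, and missing documentation is not absence of progression. The second goes beyond the trial criterion as printed and could create a new mismatch.

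**Conclusion.** The point holds as a mismatch in one stated eligibility condition. The Flatiron rule omits progression on or after 1L IO, the planned covariates cannot recover it, the limitations do not mention it, and the shell row presumes it. The IO-pretreated strata may therefore not be comparable.

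Under the assumed inputs the HR is multiplied by about 1.01 to 1.08, before adjustment for other covariates. The upward direction rests on the assumption that patients who stopped IO without progressing have the better prognosis, and the size rests on shares that the documents do not give. The possible bias is small to moderate. The correction should be made because the rule departs from the plan's own aim of alignment and the remedy is cheap.

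**What to change.** Reconcile the COLUMBUS and Flatiron criteria in Section 8.2.1 with Appendix Table 1, and state whether progression on or after 1L IO can be ascertained in Flatiron before the index date.

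- **If it can:** apply the same condition to the Flatiron cohort, fill the shell row from the checked criterion, and analyse patients with prior IO but no documented progression in a sensitivity analysis.
- **If it cannot:** relabel the Flatiron row as *Prior 1L IO*, list the gap in Section 8.9 as is done for RECIST, and add a sensitivity analysis of the adjusted overall survival comparison restricted to treatment-naive patients in both cohorts. That restriction needs no progression data.

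In either case, state in the Flatiron criterion whether 1L IO means 1L IO only, in line with the trial's rule. This is a clarification. It is useful because Table 1 gives chemotherapy as an example of prior systemic therapy, which fits neither category of the criterion.

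The cost is one reworded criterion or one added limitation, one shell label and one sensitivity analysis on existing records. The downside is fewer Flatiron patients if the condition is applied, and lower precision in the treatment-naive analysis.
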